Clinical Trial Protocol

Investigational product	Da Vinci SP Surgical System	
Study Code	TASP-UTUC	
Title	A Pilot Study of Single-Port Robot-Assisted Surgery Using Da Vinci SP Surgical System for Patients with Upper Tract Urothelial Cancer	
Clinical Phase	N.A.	
Principal Investigator	
[name] [name], PhD
 
Professor and Chairman, Department of Urology, College of Medicine, National Taiwan University, Taiwan
 
Director, Department of Urology, National Taiwan University Hospital, Taiwan
	
Sponsor	National Taiwan University Hospital, Taipei, Taiwan	
Version and Date	Version: 1	Date: Oct 17, 2024
Status	Final	

Synopsis

Investigational product	Da Vinci SP Surgical System
Study Code	TASP-UTUC
Title:	A Pilot Study of Single-Port Robot-Assisted Surgery Using Da Vinci SP Surgical System for Patients with Upper Tract Urothelial Cancer
Objectives:	
 • Primary objective To investigate clinical feasibility of radical nephroureterectomy and bladder cuff resection using single-port robotic surgery • Secondary objectives To evaluate safety, surgical outcomes, patient characteristics, and patient-reported outcomes of radical nephroureterectomy using single-port robotic surgery
Eligibility:	
Inclusion criteria:
 
 1. Age 20 years or more 2. Histologically or cytologically diagnosed upper tract urothelial cancer 4. Fitting indications of radical nephroureterectomy and ipsilateral bladder cuff resection, and deemed feasible for robotic surgery 5. ASA physical status classification 1-2 and adequate organ function 6. Patients willing and able to comply with study protocol requirements and follow-up 7. With informed consent 
Exclusion criteria:
 
 1. Synchronous bladder cancer 2. Distant metastasis of cancer 3. $BMI \geq 30$ or $BMI < 18.5$ 4. Unable to tolerate lateral decubitus or Trendelenburg position (relative contra-indication) 5. Severe adhesion due to prior abdominopelvic surgery (relative contra-indication) 6. Previous radiation treatment to the pelvic area 7. Active infectious disease

Study: TASP-UTUC

Version: 1

Date: 17/10/2024

NTUH Clinical Trial Protocol

	
8. Severe concomitant illness that drastically shortens life expectancy or increases risk of therapeutic interventions, such as: severe heart disease (NYHA functional class III-IV) or severe lung disease (GOLD Group C-D)9. Cannot follow trial-required procedures10. Concomitant systemic or pelvic disease that increases the risk of surgery11. Long-term use of anti-coagulant(s)12. Patients with coagulopathy13. Emergency surgery
Design of trial:	
• Prospective• Interventional• Open label• Single arm• Study period: 2 years (From Dec/1/2024 to Nov/30/2026)• Study site: single center study
Study treatment:	Radical nephroureterectomy and ipsilateral bladder cuff resection using da Vinci SP Surgical System (robotic surgery)
Primary endpoint:	Success without conversion to alternative surgery
Statistical analysis and sample size estimation:	
• Statistical methods: Descriptive methods will be used.• Interim analysis: No• Efficacy assessment group: Per Protocol• Estimated sample size:
○ Enroll: 25○ Evaluable: 20

Table of Content

Clinical Trial Protocol.....	1
Synopsis	2
Table of Content.....	4
Abbreviations.....	6
1. Introduction	7
1.1 Background and rationale	7
1.1.1 Medical background	7
1.1.2 Animal and preclinical study	8
1.2 Investigational product	8
1.3 Risks and benefits assessment	9
1.4 Regulatory	10
2. Objectives and Endpoints.....	10
2.1 Study objectives	10
2.1.1 Primary objective	10
2.1.2 Secondary objectives.....	10
2.1.3 Other exploratory objectives (if any).....	10
2.2 Study endpoints.....	10
2.2.1 Primary endpoint.....	10
2.2.2 Secondary endpoints	10
2.2.3 Other exploratory endpoints (if any).....	10
3. Study Design.....	11
3.1 Overall design.....	11
3.1.1 Recruitment plan.....	11
3.2 Study calendar.....	12
3.3 Criteria of Termination of the Trial.....	13
4. Study Population	13
4.1 Inclusion criteria	13
4.2 Exclusion criteria.....	13
4.3 Withdrawal criteria.....	13
5. Treatment	14

Study: TASP-UTUC

Version: 1

Date: 17/10/2024

NTUH Clinical Trial Protocol

5.1	Treatment administration	14
5.2	Concomitant therapy	14
6.	Efficacy Assessments	14
7.	Safety Assessments.....	15
8.	Adverse Event Reporting.....	15
8.1	Definitions and reports of adverse events.....	15
8.2	Serious Adverse Events.....	16
8.3	Adverse event follow-up	16
9.	Statistical Considerations.....	16
9.1	Sample size determination.....	16

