2.2 Study endpoints

2.2.1 Primary endpoint

Successful completion of RNU+ BCR without conversion to alternative surgery

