4.3 Withdrawal criteria

1. Patients refuse to continue follow up per protocol during the study period
2. Patients developing mortality or morbidity during or within 30 days after the surgery that do not have consequential correlations with the surgical procedures (such as those resulting from natural disaster, war, or unexpected accidents)

5. Treatment

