5.2 Concomitant therapy

Medical treatment of underlying chronic diseases (such as diabetes or hypertension) is allowed.

6. Efficacy Assessments

- Primary endpoint: Success without conversion to alternative surgery: successful completion of radical nephroureterectomy and bladder cuff resection with da Vinci SP system (no conversion to conventional laparoscopic, multiport da Vinci surgery or open surgery; addition of access port to complete the procedure would not be considered as conversion.)
- Operative time (min): first skin incision to closure of wound
- Console time (min): the time when the surgeon starts the console work till the specimen is taken out from the patient
- Estimated blood loss (mL): measured at operating suite
- Length of hospital stay (day): the duration from operation day to the discharge day (included)
- Pain score: measured by Visual Analogue Scale (VAS)

Other assessments:

- Patient demographics and medical history
- Pathology assessment
- Body mass index, body weight
- Analgesic use/types: opioid or non-opioid, changes in post-operative period)

Study: TASP-UTUC

Version: 1

Date: 17/10/2024

NTUH Clinical Trial Protocol

7. Safety Assessments

- Safety labs (complete blood count and other routine tests)
- Estimated blood loss (mL): measured at operating suite.
- Transfusion: record of blood product received.
- Complication (intraoperative and/or postoperative) (Clavien Dindo grading)
- Readmission (in 30 days)
- Reoperation (in 30 days)
- Perioperative mortality (in 30 days)

8. Adverse Event Reporting

Upon the occurrence of serious adverse events (SAE) which result in serious malfunctioning of the medical device, [name] [name] will report SAEs to the IRB of NTUH according to the Serious Adverse Event Reporting Procedures and Guidelines posted by NTUH. SAE reports to the IRB should include the following information when calling the Medical Monitor:

- Date and time of the SAE
- Date and time of the SAE report
- Name of reporter
- Call back phone number
- Affiliation/Institution conducting the study
- Protocol number
- Title of protocol
- Description of the SAE, including attribution to drug and expectedness

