9.2.1 Efficacy analysis

Success rate for the completion of radical nephroureterectomy and bladder cuff resection with da Vinci SP System without conversion will be presented as proportions.

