9.2.2 Safety analysis

All operated patients will be included in safety analysis. Related AE and complications will be described.

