9.2.3 Analysis population

All operated patients will be included in analysis.

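### The protocol names two different populations for its single primary endpoint: Per Protocol in the synopsis, all operated patients in Section 9.2.3

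*Protocol*

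**What the plan says.** The primary endpoint (Section 2.2.1) is "Successful completion of RNU+ BCR without conversion to alternative surgery". Section 6 makes the failure event explicit: success requires "no conversion to conventional laparoscopic, multiport da Vinci surgery or open surgery", and an added access port does not count as a conversion.

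Four statements bear on who is analysed:

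- Synopsis, statistical analysis and sample size entry: "Efficacy assessment group: Per Protocol".
- Section 9.2.1, efficacy: "Success rate for the completion of radical nephroureterectomy and bladder cuff resection with da Vinci SP System without conversion will be presented as proportions". No denominator is named.
- Section 9.2.2, safety: "All operated patients will be included in safety analysis".
- Section 9.2.3, analysis population: "All operated patients will be included in analysis".

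Section 9 does not mention a Per Protocol set. Section 4.3 also lists a withdrawal criterion that can apply after surgery: "Patients refuse to continue follow up per protocol during the study period".

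**The concern.** The synopsis and Section 9.2.3 name different populations, and both apply to the primary success rate. Nothing in the protocol says which prevails or that they are the same patients.

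This matters more than usual because of what the endpoint measures. The study treatment is nephroureterectomy and bladder cuff resection with the SP system. A converted patient did not complete that treatment, so conversion could be read as a departure from protocol. On that reading a Per Protocol set drops the failures, and the success rate is 100% by construction. Operated patients withdrawn under Section 4.3 could also be dropped, although their conversion status is known when the operation ends.

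The trial is open label with one arm. With two populations on paper, the denominator could be chosen once the conversions are known.

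**Working it through.** **Comparing the statements.** Section 9.2.3 cannot be set aside as the safety population, because Section 9.2.2 already defines that one. Section 9.2.1 leaves the denominator open. Only the synopsis line and Section 9.2.3 could supply it, and they differ. Both stand in the current Version 1 text.

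**The plan's own figures.** Section 3.1.1 gives 20 evaluable patients plus 5 screening failures and drop-outs, and 20 + 5 = 25 agrees with the stated enrolment. The 20 has no formula behind it (Section 9.1), so there is no power or error rate to reproduce.

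**Inputs for the illustration.**

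- n = 20 operated patients. This takes the synopsis figure for evaluable patients as the number operated, which is an assumption.
- c = number of conversions. The protocol gives no expected rate, so c = 0, 1, 2 and 5 are assumed.

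**Formulas.** All operated: (20 − c)/20. Conversions excluded: (20 − c)/(20 − c) = 1 for any c. Intervals are exact (Clopper-Pearson) 95%. When all m patients succeed, the lower limit is 0.025^(1/m); for m = 20 this is 83.2%.

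| Conversions | All operated (95% CI) | Conversions excluded (95% CI) | Gap, points |
|---|---|---|---|
| 0 | 20/20 = 100% (83.2–100) | 20/20 = 100% (83.2–100) | 0 |
| 1 | 19/20 = 95% (75.1–99.9) | 19/19 = 100% (82.4–100) | 5 |
| 2 | 18/20 = 90% (68.3–98.8) | 18/18 = 100% (81.5–100) | 10 |
| 5 | 15/20 = 75% (50.9–91.3) | 15/15 = 100% (78.2–100) | 25 |

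**Withdrawal only.** Suppose Per Protocol keeps conversions but drops one withdrawn patient, with 2 conversions among 20 (18/20 = 90.0%):

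- dropping one converted patient gives 18/19 = 94.7% (74.0–99.9);
- dropping one patient who was not converted gives 17/19 = 89.5% (66.9–98.7).

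Withdrawal can therefore move the rate either way, by much less than excluding all conversions would when there are several.

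**The case against.** The strongest reply is that the two labels may mean the same patients. In the synopsis the Per Protocol line stands just above the figures of 25 enrolled and 20 evaluable. In a single-arm trial of one operation it could simply mean those who received the study operation, as against everyone screened. The two rates would then be identical. The illustration itself equates evaluable with operated. This reading is possible, but the protocol does not state it.

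It can also be said that excluding conversions runs against the document. Conversion is the defined failure, it is listed as an anticipated risk in Section 1.3, it is absent from the withdrawal criteria, and a success rate without conversions would be empty. This has force: Section 6 suggests that conversions are meant to count. The 100% result is therefore an extreme reading, not what the plan prescribes.

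The withdrawal route is weaker still. Section 4.3 does not say that collected data are discarded, and Section 9.2.4 excludes only missing data.

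Finally, an SAP may define Per Protocol in advance. That would answer a complaint about a missing definition. It would not answer this one, because an SAP that chose either population would still contradict the other protocol statement.

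**Conclusion.** The concern holds. The protocol contradicts itself on the population for its only primary result, and it should be corrected. Confidence is high for the contradiction itself.

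The size depends on the reading. If Per Protocol removes conversions, the reported success rate is overstated by 5 to 25 percentage points for 1 to 5 conversions in 20. If it removes only an occasional withdrawn patient, the shift is small and can go either way. If it removes no operated patient, or no conversion occurs and so no failure is recorded, there is no difference. The conversion counts and the 20 operated patients are assumptions.

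The analysis is descriptive, with no formal test and no success threshold, so no decision rule or error rate is affected. What is at stake is whether the feasibility estimate can be trusted as planned in advance.

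**What to change.** 1. **Synopsis:** change the efficacy assessment group to all operated patients, matching Section 9.2.3.
2. **Section 9.2.1:** state that the denominator is all operated patients and that every conversion as defined in Section 6, and every abandoned procedure, counts as a failure.

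These two changes resolve the conflict. Three additions would close the remaining gaps:

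3. **Section 9.2.3:** count a patient as operated from the first skin incision for the planned SP procedure. Section 6 already starts operative time there ("first skin incision to closure of wound"). In Section 5.1 the incision and retroperitoneal access come before port insertion, so a case converted during access stays in.
4. **Section 9.2.1, with a cross-reference in 4.3:** state that withdrawal after surgery does not remove a patient from the primary endpoint.
5. **Any Per Protocol rate:** define it in advance and report it as supplementary only.

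The cost is a short text amendment to the synopsis and Sections 4.3, 9.2.1 and 9.2.3. It needs no extra patients or data. The reported success rate may be lower than under a Per Protocol set that left conversions out.

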1.1 Background and rationale

1.1.1 Medical background

Upper tract urothelial cancers (UTUC), including cancers of renal pelvis and ureter (ICD-10 codes: C65 and C66), are relatively rare worldwide. UTUC accounts for less than 10% of all urothelial cancers [1]. In several aspects, UTUC in Taiwan is unique. Except Taiwan, men have higher incidence of UTUC than women. According to Cancer Incidence in Five Continents, Vol. XI [2], in the US, the annual incidence of cancer of renal pelvis in men was 0.6 per 100,000 population during year 2008-2012. During the same period, the incidence of cancer of renal pelvis in Taiwanese men was 2.1. It is noteworthy that Taiwanese females had extraordinarily high incidence of 2.1 per 100,000 population. Regarding cancer of ureter, both men and women in Taiwan have higher incidence than most western populations, 1.1 and 1.4 per 100,000 population, respectively [3]. The high incidence of UTUC in Taiwan has been attributed to several potential etiologies, including smoking, exposure to aristolochic acid, genetic factors, occupational exposures such as aromatic amines, and environmental factors such as Arsenic [4,5]. Due to these unusual features of UTUC in Taiwan, significant has been undertaken [6]. Our group has published several research of surgical techniques for this important endemic cancer [7-14].

For localized high risk UTUC, the curative treatment option is radical nephroureterectomy (RNU) plus bladder cuff resection (BCR) with/without template lymphadenectomy [15-17]. Although European Association of Urology (EAU) guideline recommends open RNU as standard treatment, in the modern era of minimally invasive care, laparoscopic RNU+BCR with/without robotic assistance is feasible. In experienced hands, both laparoscopic and robotic RNU+ BCR provide similar oncological outcomes as open RNU. In addition, robotic RNU+BCR can limit the risk of post-operative complications and shorten hospital stay [16]. However, the EAU guideline provides precautions for minimally invasive RNU to minimize tumor spread along trocar routes as some reports have shown tumor metastasis under pneumoperitoneum condition during laparoscopic surgery [16,18,19].

Laparoscopic surgery is the most popular minimally invasive surgery (MIS) technique adopted for RNU+ BCR. However, laparoscopic RNU+ BCR is accompanied by barriers such as complex manipulation of instruments and challenging learning curve, especially for BCR. These barriers sometimes make surgeon to performed open or hybrid surgery. In a recent study, out of 1,808 patients with UTUC who underwent RNU, open surgery and laparoscopic hand-assisted were performed in 21.1% and 42.5%, respective. Total MIS either using robotic or laparoscopic RNU were done for 8.7% and 27.3%, respectively [6].

With the adoption and popularity of robotic surgery in urological area, RNU+ BCR has increasingly been done by robotic surgery. Some changes have been brought into the practice of robotic RNU+ BCR compared to traditional open approach. The most prominent changes are transperitoneal approach rather than retroperitoneal approach and flank rather than supine position. These modifications are advantageous for better visualization of anatomic landmark, larger space for multiple arms of robotic platform, and shorter learning curve [20,21].

Transperitoneal robotic partial nephrectomy is a well-established standard robotic procedure [22]. However, there are challenges when applying transperitoneal techniques in RNU. Due to the multi-quadrant nature of UTUC, patients sometimes need to be repositioned from flank to supine and robotic system requires re-docking. These procedures will lengthen the operation time. When working in limited

Study: TASP-UTUC

Version: 1

Date: 17/10/2024

NTUH Clinical Trial Protocol

operation space, external clashing of robotic arms cannot be fully avoided. It is because the multi-arm design of the commonly used robotic surgical system. Another drawback of multi-arm robotic system is the requirement of 4 to 6 access ports on abdominal wall, i.e. more surgical wounds are created. Some rarely addressed topics are related to the shift from retroperitoneal to transperitoneal access. Now, there is an emerging trend back to retroperitoneal access for RNU+BCR with the novel single-port surgical system [20,21]. Some evidence supported the retroperitoneal access: less blood loss, shorter operation time and shorter hospitalization time [22]. More same-day discharges can be achieved by single-port system [23]. These advantages of retroperitoneal approach can only be implemented with the novel single-port system for easier manipulation within limited working space.

Recently, [name] group developed a new technique of robotic RNU using single-port system, supine anterior retroperitoneal access (SARA) [20,21]. Briefly, patient is placed in supine position, a 3-cm incision is made at the McBurney point, and the da Vinci SP Surgical System is used to complete total robotic RNU+ BCR. Case reports from 2 patients showed low complication rate, less post-operative pain, and shorter hospitalization with the SARA RNU. With supine retroperitoneal approach, there is no need of patient reposition and re-docking of robot. Above-mentioned advantages of retroperitoneal access can be potentially achieved. Less respiratory stress is expected for the absence of pneumoperitoneum and lateral decubitus position [21].

In the initial report of 18 patients, 12 were partial nephrectomy, 2 each for radical nephrectomy, pyeloplasty, and nephroureterectomy [21]. Larger study of SARA technique is necessary for RNU+ BCR to verify its feasibility, safety and to identify its limitation(s) and areas for further potential improvement. Considering the current technical challenges of performing laparoscopic RNU+BCR or multiport robotic surgery in UTUC (a condition with higher incidence rates in Taiwan), this study is set forth to the above-mentioned goals of SARA RNU+ BCR using da Vinci SP system.

1.1.2 Animal and preclinical study

Prior to use SARA in human patients, the SP system has been evaluated for several operations in cadaveric models to determine the feasibility and technical approach that would be most advantageous for this system [24-27]. Given the ability of the SP system to operate within a small operative radius, this study aims to evaluate the performance and safety of the da Vinci SP® Surgical System for the surgical treatment of UTUC.

1.2 Investigational product

Da Vinci SP Surgical System, Model SP1098

The da Vinci SP® Surgical System, Model SP1098, uses advanced robotic technology to facilitate accurate movement of EndoWrist SP™ Instruments through a single surgical port. It is designed to enable complex surgery using a minimally invasive approach. The System includes three major subsystems (Surgeon Console, Vision Cart, Patient Cart), which are used with instruments and accessories. The system is software controlled.

The surgeon seated at the Surgeon Console controls all movement of the instruments and camera by using two hand controls and a set of foot pedals. The surgeon views the camera image on a three-dimensional (3D) viewer, which provides a view of patient anatomy and instrumentation, along with icons and other user interface features.

Study: TASP-UTUC

Version: 1

Date: 17/10/2024

NTUH Clinical Trial Protocol

The Vision Cart includes supporting electronic equipment, such as the camera light source, video and image processing, and the networking hardware. The Vision Cart also has a touchscreen to view the camera image and adjust system settings.

The Patient Cart is the operative component of the da Vinci SP Surgical System. Its primary function is to support the positioning of the surgical port and to manipulate the surgical instruments and camera. The Patient Cart is positioned at the operating room table and contains an instrument arm that is positioned with respect to the target patient anatomy. The instrument arm contains four instrument drives that hold up to three surgical instruments and the camera. The patient-side assistant installs and removes the camera and instruments intra-operatively.

EndoWrist SP® Instruments:

Intuitive Surgical® EndoWrist SP Instruments are controlled by the da Vinci SP Surgical System, Model SP1098, and include flexible endoscopes, blunt and sharp endoscopic dissectors, scissors, forceps/pick-ups, needle holders, endoscopic retractors, electrocautery and accessories for endoscopic manipulation of tissue, including grasping, cutting, blunt and sharp dissection, approximation, ligation, electrocautery, and suturing through a single port.

The EndoWrist SP® Instruments and the catalog number used in this trial are listed below:

SP Endoscope (430077)

Monopolar Curved Scissors (a.k.a MCS) and MCS Tip (430004/430035)

Monopolar cautery instrument & hook (430007/400156)

Fenestrated bipolar forceps (430011)

Round tooth retractor (430002)

Medium-Large Clip Applier (430005)

Needle driver (430006)

Cadiere Forceps (430009)

Maryland bipolar forceps (430010)

